7.2.3.2 Analytical method

An ELISA method will be used for bioanalytical analysis of ACZ885 in serum, with an anticipated lower limit of quantification (LLOQ) of 100 ng/mL for samples analyzed in China and 300 ng/mL for all other samples. The detailed method description to assess ACZ885 concentration will be described in the bioanalytical raw data of the study and in the respective Bioanalytical Data Report (BDR).

A Meso Scale Discovery (MSD) electrochemiluminescence assay based method will be used for the detection of potential anti-ACZ885 antibody formation. The detailed method description to assess immunogenicity will be described in the bioanalytical raw data of the study and in the respective BDR.

An ELISA method will be used for bioanalytical analysis of total IL-1 β in serum, with an anticipated LLOQ of 0.299 ng/mL. The detailed method description to assess PD concentration will be described in the bioanalytical raw data of the study and in the respective BDR.

7.2.4.2 Biomarker sample collection sub-study (CACZ885T2301A) in non-small cell lung cancer subjects that are candidates for curative surgery*

NSCLC subjects who are candidates for complete resection surgery (and therefore, prospective candidates for the main study, CACZ885T2301) will be asked to participate in a biomarker substudy (CACZ885T2301A). In this sub-study, pre- and post-surgery blood samples will be collected to evaluate biomarkers involved in the IL-1 β inflammatory pathway as well as mutations present in blood prior to surgery (see Table 7-2).

The sub-study will be identified as CACZ885T2301A. Signature of a separate informed consent form will be required before any samples are collected. Lack of participation in the sub-study does not exclude subject's ability to participate in the main study, CACZ885T2301.

Enrollment into the sub-study will end when the enrollment into the main study has been completed.

The scope of this sub-study is limited to the collection of samples as described in Table 7-2.

Data for this sub-study will be collected in a separate database with unique subject IDs (Refer to Section 6.5.1).

*For China only: biomarker collection is conditional upon approval from HA, EC and additional authorities (i.e. HGRAC).

7.2.5 Other assessments

7.2.5.1 Anti-ACZ885 antibodies (immunogenicity assessment)

To assess potential immunogenicity, serum samples for determination of anti-canakinumab antibodies will be collected during the study according to the visit schedule outlined in Table 7-1.

7.2.6 Patient reported outcomes

7.2.6.1 PRO Questionnaires

The European Organization for Research and Treatment of Cancer's core quality of life questionnaire EORTC-QLQC30 (version 3.0) and it's lung cancer specific module QLQ-LC13 (version 1.0) will be used to collect data on the subject's functioning, disease-related symptoms, health-related quality of life, and health status. The EQ-5D-5L will be used for the purpose of the computation of utilities that can be used in health economic studies. The EORTC QLQ-C30/LC13 as well as the EQ-5D-5L are reliable and valid measures frequently used in clinical

trials of subjects with lung cancer and previously used in the adjuvant setting (Bezjak et al 2008).

The EORTC-QLQC30 is a self-reporting 30-item generic instrument for use in cancer subjects across tumor types including lung cancer. It assesses 15 domains consisting of 5 functional domains (physical, role, emotional, cognitive, social) and 9 symptom domains (fatigue, nausea and vomiting, pain, dyspnea, insomnia, appetite loss, constipation, diarrhea, financial difficulties) and a global health status or HRQoL scale (Aaronson et al 1993). The EORTC QLQ-LC13 complements the QLQ-C30, and measures disease symptoms and treatment-related adverse effects. The lung cancer module incorporates one multi-item scale to assess dyspnea, and 9 single items assessing pain, coughing, sore mouth, dysphagia, peripheral neuropathy, alopecia, and hemoptysis (Bergman et al 1994).

All of the domain scores of the EORTC-QLQC30 and QLQ-LC13 range from 0 to 100. A high score indicates a higher response level. Hence, a high score for a functional scale indicates a high and healthy level of functioning but a high score for a symptom scale indicates a high level of symptoms/problems.

The EQ-5D-5L is a standardized measure of health status developed by the EuroQol Group in order to provide a simple, generic measure of health for clinical and economic appraisal (EuroQol Group 1990). The EQ-5D-5L is designed for self-completion by respondents and takes only a few minutes to complete. Instructions to respondents are included in the questionnaire. The EQ-5D-5L consists of 2 pages – the descriptive system and the EQ visual analogue scale (EQ VAS) (Herdman M et al 2011). The descriptive system comprises 5 dimensions (mobility, self-care, usual activities, pain/discomfort, and anxiety/depression), each with 5 levels: no problems, slight problems, moderate problems, severe problems, and extreme problems. The EQ VAS records the respondent's self-rated health on a 20 cm vertical, visual analogue scale with endpoints labeled 'the best health you can imagine' and 'the worst health you can imagine'.

7.2.6.2 PRO assessments

PRO questionnaires (EORTC QLQ-C30/LC13 and EQ-5D-5L) will be provided at the visits indicated in Table 7-1, i.e. at screening, after randomization every 3 weeks for 18 cycles, at EOT, every 4 weeks during the 130-day safety follow up, every visit before any radiological assessment is done for recurrence, before any unscheduled imaging assessments and two follow up visits after documented disease recurrence (one within 7 days and one within 28 days after discussing disease recurrence with the subject).

All questionnaires should be provided in the subject's local language at the beginning of the study visit prior to any interaction with the study investigator including any tests, treatments or receipt of results from any tests to avoid biasing the subject's perspective. This is to avoid potentially biasing subjects or their responses to study questionnaires.

PRO data will be recorded by subjects onto an electronic tablet device maintained at the study site. Investigators or study personnel should provide technical assistance but should not encourage the subjects to change responses reported in questionnaires.

Subjects should be given sufficient space and time to complete all study questionnaires. Subjects should be encouraged to complete any missing responses. Attempts should be made to collect responses to all questionnaires for all subjects, including from those who discontinue prior to the study evaluation completion visit, however, if subjects refuse to complete questionnaires, this should be documented in study source records. Subjects' refusal to complete study questionnaires are not protocol deviations.

Questionnaires should be completed before any other clinical assessments planned for the study visit.

8 Safety monitoring and reporting

8.1 Adverse events

8.1.1 Definitions and reporting

An adverse event is defined as the appearance of (or worsening of any pre-existing) undesirable sign(s), symptom(s), or medical condition(s) that occur after a subject's signed informed consent has been obtained.

Abnormal laboratory values or test results occurring after informed consent constitute adverse events only if they induce clinical signs or symptoms, are considered clinically significant, require therapy (e.g., hematologic abnormality that requires transfusion or hematological stem cell support), or require changes in study medication(s).

Adverse events that begin or worsen after informed consent should be recorded in the AE eCRF. Conditions that were already present at the time of informed consent should be recorded in the medical history eCRF. Adverse event monitoring should be continued for at least 130 days following the EOT visit. Adverse events (including lab abnormalities that constitute AEs) should be described using a diagnosis whenever possible, rather than individual underlying signs and symptoms. When a clear diagnosis cannot be identified, each sign or symptom should be reported as a separate Adverse Event.

If a new antineoplastic therapy is initiated after discontinuation of study treatment, only SAEs suspected to be related to study treatment will be collected in the Adverse Events eCRF.

Confidential

Adverse events will be assessed and graded according to the Common Terminology Criteria for Adverse Events (CTCAE) version 5.0.

If CTCAE grading does not exist for an adverse event, the severity of mild, moderate, severe, and life-threatening, death related to the AE corresponding respectively to Grades 1 - 5, will be used. Information about any deaths (related to an adverse event or not) will also be collected though a death form.

The occurrence of adverse events should be sought by non-directive questioning of the subject during the screening process after signing informed consent and at each visit during the study. Adverse events also may be detected when they are volunteered by the subject during the screening process or between visits, or through physical examination, laboratory test, or other assessments. As far as possible, each adverse event should be evaluated to determine:

- The severity grade (CTCAE v5.0 Grades 1-5)
- Its duration (Start and end dates)
- Its relationship to the study treatment. Reasonable possibility that AE is related:
 - No (i.e. not treatment-related);
 - Yes, investigational treatment (i.e. related to treatment with canakinumab/placebo);
- Action taken with respect to study or investigational treatment (none, dose adjusted, temporarily interrupted, permanently discontinued, unknown, not applicable)
- Whether medication or therapy was given (no concomitant medication/non-drug therapy, concomitant medication/non-drug therapy)
- Whether it is serious, where an SAE is defined as in Section 8.2.1 and which seriousness criteria have been met
- Outcome (not recovered/not resolved, recovering/resolving, recovered/resolved, recovered/resolved with sequelae, fatal, unknown)

If the event worsens the event should be reported a second time in the eCRF noting the start date when the event worsens in toxicity. For grade 3 and 4 adverse events only, if improvement to a lower grade is determined a new entry for this event should be reported in the eCRF noting the start date when the event improved from having been Grade 3 or Grade 4.

All adverse events should be treated appropriately. If a concomitant medication or non-drug therapy is given, this action should be recorded on the AE eCRF.

Once an adverse event is detected, it should be followed until its resolution or until it is judged to be permanent, and assessment should be made at each visit (or more frequently, if necessary) of any changes in severity, the suspected relationship to the study treatment, the interventions required to treat it, and the outcome.

8.1.2 Laboratory test abnormalities

8.1.2.1 Definitions and reporting

Laboratory abnormalities that constitute an adverse event in their own right (are considered clinically significant, induce clinical signs or symptoms, require concomitant therapy or require changes in study treatment), should be recorded on the AE eCRF. Whenever possible, a diagnosis, rather than a symptom should be provided (e.g. anemia instead of low hemoglobin). Laboratory abnormalities that meet the criteria for adverse events should be followed until they have returned to normal or an adequate explanation of the abnormality is found. When an abnormal laboratory or test result corresponds to a sign/symptom of an already reported adverse event, it is not necessary to separately record the lab/test result as an additional event.

Laboratory abnormalities that do not meet the definition of an adverse event should not be reported as adverse events. A Grade 3 or 4 event (severe) as per CTCAE does not automatically indicate a SAE unless it meets the definition of serious as defined below and/or as per investigator's discretion. A dose hold or medication for the lab abnormality may be required by the protocol in which case the lab abnormality would still, by definition, be an adverse event and must be reported as such.

8.1.3 Adverse events of special interest

Adverse events of special interest (AESI) are defined as events (serious or non-serious) which are ones of scientific and medical concern specific to the sponsor's product or program, for which ongoing monitoring and rapid communication by the investigator to the sponsor may be appropriate. Such events may require further investigation in order to characterize and understand them.

Adverse events of special interest are defined on the basis of an ongoing review of the safety data and include:

- infections/opportunistic infections,
- neutropenia,
- abnormal liver parameters,
- thrombocytopenia,
- immunogenicity/allergenicity,
- autoimmunity reactions,
- new primary malignancy,
- interactions with vaccines,
- interactions with drugs eliminated by CYP450 enzymes,
- pulmonary complications (pulmonary hypertension and interstitial lung disease)
- injection site reactions.

Details regarding these adverse events are provided in the [canakinumab Investigator's Brochure]. Potential emergent new AEs will be monitored during the course of the study.

Canakinumab is associated with an increased incidence of serious infections during and after treatment. Therefore subjects should be carefully monitored for signs and symptoms of

infections during and after treatment with canakinumab. Physicians should exercise caution when administering canakinumab to subjects with infections, a history of recurring infections, or underlying conditions which may predispose them to infection.

Neutropenia has been observed with medicinal products that inhibit IL-1 β , including canakinumab.Treatment should not be initiated in subjects with neutropenia. It is recommended that neutrophil counts be assessed before and during treatment.

8.2 Serious adverse events

8.2.1 Definitions

An SAE is defined as any adverse event [appearance of (or worsening of any pre-existing)] undesirable sign(s), symptom(s) or medical conditions(s) which meets any one of the following criteria:

- Is fatal
- Life-threatening

Note: Life-threatening in the context of a SAE refers to a reaction in which the subject was at risk of death at the time of the reaction; it does not refer to a reaction that hypothetically might have caused death if it were more severe (please refer to the ICH-E2D Guidelines).

- Results in persistent or significant disability/incapacity
- Constitutes a congenital anomaly/birth defect, fetal death or a congenital abnormality or birth defect
- Requires in subject hospitalization or prolongation of existing hospitalization,
- Note that hospitalizations for the following reasons should not be reported as serious adverse events:
 - Routine treatment or monitoring of the studied indication, not associated with any deterioration in condition
 - Elective or pre-planned treatment for a pre-existing condition that is unrelated to the indication under study and has not worsened since signing the informed consent
 - Social reasons and respite care in the absence of any deterioration in the subject's general condition
 - Treatment on an emergency outpatient basis for an event not fulfilling any of the definitions of a SAE given above and not resulting in hospital admission
- Is medically significant, i.e., defined as an event that jeopardizes the subject or may require medical or surgical intervention to prevent one of the outcomes listed above

Medical and scientific judgment should be exercised in deciding whether other situations should be considered serious reactions, such as important medical events that might not be immediately life threatening or result in death or hospitalization but might jeopardize the subject or might require intervention to prevent one of the other outcomes listed above. Such events should be considered as "medically significant". Examples of such events are intensive treatment in an emergency room or at home for allergic bronchospasm, blood dyscrasias or convulsions that do not result in hospitalization or development of dependency or abuse (please refer to the ICH-E2D Guidelines).

Confirmed COVID-19 infection should be considered as medically significant and should therefore be reported as an SAE.

All new malignant neoplasms will be assessed as serious under "medically significant" if other seriousness criteria are not met and the malignant neoplasm is not a disease progression of the study indication.

Any suspected transmission via a medicinal product of an infectious agent is also considered a serious adverse reaction.

All reports of intentional misuse and abuse of the product are also considered serious adverse event irrespective if a clinical event has occurred.

8.2.2 SAE Reporting

To ensure subject safety, every SAE, regardless of causality, occurring after the subject has provided informed consent and until at least 130 days after the subject has stopped study treatment must be reported to Novartis safety immediately, without undue delay, but under no circumstances later than within 24 hours of obtaining knowledge of the events (Note: If more stringent, local regulations regarding reporting timelines prevail). Detailed instructions regarding the submission process and requirements are to be found in the investigator folder provided to each site. Information about all SAEs is collected and recorded on the eSAE Serious Adverse Event Report Form; all applicable sections of the form must be completed in order to provide a clinically thorough report. In case of technical issue to report SAE information via eSAE, the site must complete paper SAE form to meet 24-hour reporting timeline; once the issue is resolved, the site must enter the SAE information in eSAE database.

If a new antineoplastic therapy is initiated after discontinuation of study treatment, only SAEs suspected to be related to study treatment will be collected in the Adverse Events eCRF.

For SAE reporting in case of malignancies during the study, the following applies:

- Recurrence of NSCLC malignancy (including fatal outcomes), if documented by use of appropriate method (for example, as per RECIST criteria for solid tumors), should not be reported as a serious adverse event, except if the investigator considers that progression of malignancy is related to study treatment. Adverse events separate from the recurrence of NSCLC malignancy (example, deep vein thrombosis at the time of recurrence or hemoptysis concurrent with finding of disease recurrence) will be reported as per usual guidelines used for such events with proper attribution regarding relatedness to the drug.
- New primary lung cancer malignancies should always be reported as SAEs.
- New primary malignancies in organs other than lung should always be reported as SAEs.

Any additional information for the SAE including complications, progression of the initial SAE, and recurrent episodes must be reported as follow-up to the original episode immediately, without undue delay, but under no circumstances later than within 24 hours of the investigator receiving the follow-up information (Note: If more stringent, local regulations regarding reporting timelines prevail). An SAE occurring at a different time interval or otherwise considered completely unrelated to a previously reported one should be reported separately as a new event.

Any SAEs experienced after the 130-day safety follow-up period should only be reported to Novartis if the investigator suspects a causal relationship to the study treatment.

Confidential

Information about all SAEs is collected and recorded on the Serious Adverse Event Report Form; all applicable sections of the form must be completed in order to provide a clinically thorough report. The investigator must assess and record the relationship of each SAE to each specific study treatment (if there is more than one study treatment), complete the SAE Report Form in English, and submit the completed form within 24 hours to Novartis. Detailed instructions regarding the SAE submission process and requirements for signatures are to be found in the investigator folder provided to each site.

Follow-up information is submitted in the same way as the original SAE Report. Each reoccurrence, complication, or progression of the original event should be reported as a followup to that event regardless of when it occurs. The follow-up information should describe whether the event has resolved or continues, if and how it was treated, whether the blind was broken or not, and whether the subject continued or withdrew from study participation.

If the SAE is not previously documented in the Investigator's Brochure or Package Insert (new occurrence) and is thought to be related to the Novartis study treatment, an oncology Novartis Chief Medical Office and Patient Safety (CMO&PS) department associate may urgently require further information from the investigator for Health Authority reporting. Novartis may need to issue an Investigator Notification (IN), to inform all investigators involved in any study with the same drug that this SAE has been reported.

Suspected Unexpected Serious Adverse Reactions (SUSARs) will be collected and reported to the competent authorities and relevant ethics committees in accordance with EU Guidance 2011/C 172/01 or as per national regulatory requirements in participating countries.

Applicable for sub-study:

Only SAEs related to the blood sample collection in the sub-study will be collected.

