10.5.3 Safety objectives

10.5.3.1 Analysis set and grouping for the analyses

For all safety analyses, the safety set will be used. All listings and tables will be presented by treatment arm.

The overall observation period will be divided into three mutually exclusive segments:

- 1. pre-treatment period: from day of subject's informed consent to the day before first dose of study medication
- 2. on-treatment period: from day of first dose of study treatment to 130 days after last dose of study treatment
- 3. post-treatment period: starting at day 131 after last dose of study treatment.

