If subjects have no value as defined above, the baseline result will be missing.

On-treatment assessment/event and observation periods

For adverse event reporting the overall observation period will be divided into three mutually exclusive segments:

- **pre-treatment period:** from day of subject’s informed consent to the day before first administration of study treatment
- **on-treatment period:** from date of first administration of study treatment to 130 days (approximately five terminal half-lives of canakinumab) after date of last actual administration of any study treatment (including start and stop date)
- **post-treatment period:** starting at day 131 after last administration of study treatment.

Safety summaries (tables, figures) include only data from the on-treatment period with the exception of baseline data which will also be summarized where appropriate (e.g. change from baseline summaries). In addition, a separate summary for death including on treatment and post treatment deaths will be provided. In particular, summary tables for adverse events (AEs) will summarize only on-treatment events, with a start date during the on-treatment period (**treatment-emergent** AEs).

However, all safety data (including those from the post-treatment period) will be listed and those collected during the pre-treatment and post-treatment period will be flagged.

Windows for multiple assessments

Time windows will be defined for descriptive summary of PRO and ECOG performance status data by visit and longitudinal data analysis (Table 2-1). If more than one assessment is available in the same time window, the assessment closest to the planned date will be considered. If two assessments are obtained with the same time difference compared to the scheduled visit day, the assessment obtained prior to visit will be considered. Data obtained at the end of treatment will be classified as other assessment in the corresponding time window.

Table 2-1 Time windows for PRO and ECOG PS assessments

Time Window	Planned Visit Timing	Time Window Definition
Treatment phase		
Baseline	On or before Study Day 1[a]	≤ Study Day 1
Week 3	Study Day 22	Study Days 2 to 32
Week 6	Study Day 43	Study Days 33 to 53
.....
Week k (with k = 9, 12...)	Study Day 21*(k/3)+1	Study Day 21*(k/3)-9 to 21*(k/3)+11 If last dose date is in the window, upper bound of this time window will be EOT visit date +7

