2.7.3 New primary cancer other than lung cancer

Summary statistics will be tabulated for subjects with new primary cancer other than lung cancer based on "Diagnosis and extent of new primary Cancer Other than Lung" eCRF page. This analysis will include the following: number of subjects with new primary cancer, primary site of cancer, the time from randomization to initial diagnosis, predominant histology/cytology, staging system and metastatic sites.

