2.8.1.1 Adverse events of special interest / grouping of AEs

Data analysis of AESIs

An AE of special interest (AESI) is a grouping of AEs that are of scientific and medical concern specific to canakinumab. These groupings are defined using MedDRA terms, SMQs (standardized MedDRA queries), HGLTs (high level group terms), HLT (high level terms) and PTs. Customized SMQs (Novartis MedDRA queries, NMQ) may also be used. A NMQ is a customized group of search terms which defines a medical concept for which there is no official SMQ available or the available SMQ does not completely fit the need. It may include a combination of single terms and/or an existing SMQ, narrow or broad. The groups are defined according to the MedDRA terms defined in the program Case Retrieval Strategy (CRS) document and will be summarized. The latest version of the CRS document available at the time of the analyses will be used. For each specified AESI, number and percentage of subjects with at least one event of the AESI occurring during on treatment period will be summarized.

Summaries of these AESIs will be provided by treatment (specifying grade, SAE, relationship, leading to treatment discontinuation, leading to dose interruption, hospitalization, death, etc.).

A listing of all grouping levels down to the MedDRA PTs used to define each AESI will be generated.

Table 2-6 provides current AESI groupings. CRS at the time of database lock will govern how these groups will be summarized:

Table 2-6 AESI groupings

AESI grouping
Infections
Opportunistic infections
Opportunistic infections (based on SMQ Broad)

Opportunistic infections (based on SMQ Narrow)

Neutropenia

Abnormal liver parameters

Thrombocytopenia

Immunogenicity/allergenicity

Autoimmunity reactions

Malignancy

Interactions with vaccines

Pulmonary complications: pulmonary hypertension and interstitial lung disease

Injection site reactions

Time to onset of AESI

Time to onset of CTC grade ≥ 2 AESI is defined as the time from the start of treatment to the start date of the first incidence of an event of CTC grade ≥ 2 , i.e., time in days is calculated as (start date of first occurrence of the event) – (date of first dose of study treatment) +1.

In the absence of an event during the on-treatment period, the censoring date applied will be the earliest of the following dates:

- End date of on-treatment period (end of study treatment + 130 days).
- death date

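### Protocol 8.2.2 gives two incompatible rules for new primary malignancies after day 130, and the Malignancy AESI table stops at the same point, so late cancers judged unrelated can be absent from both

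*Protocol*

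**What the plan says.** New primary malignancy is an adverse event of special interest (Protocol 8.1.3; SAP Table 2-6, grouping Malignancy). The places that govern how it is reported and counted are these:

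- **Protocol 8.2.2, malignancy bullets.** "New primary lung cancer malignancies should always be reported as SAEs" and "New primary malignancies in organs other than lung should always be reported as SAEs". The lead-in applies them to malignancies during the study and sets no end date.
- **Protocol 8.2.2, later in the section.** "Any SAEs experienced after the 130-day safety follow-up period should only be reported to Novartis if the investigator suspects a causal relationship" to study treatment. Malignancy is not excepted. The adverse-event row of Table 7-1 agrees: in the post-treatment columns it asks only for treatment-related SAEs.
- **Protocol 10.5.3.1.** The on-treatment period runs "from day of first dose of study treatment to 130 days after last dose of study treatment".
- **SAP 2.1.1.** "Safety summaries (tables, figures) include only data from the on-treatment period", apart from baseline data and a separate summary of deaths. Safety data collected outside that period are listed and flagged.
- **SAP 2.8.1.1.** For each AESI, the "number and percentage of subjects with at least one event of the AESI occurring during on treatment period will be summarized".
- **SAP 2.7.3.** "Summary statistics will be tabulated for subjects with new primary cancer other than lung cancer", taken from a dedicated eCRF page, including time from randomization to diagnosis. No 130-day limit is stated.
- **Protocol 10.4.1 and SAP 2.5.1.** A new primary lung malignancy counts as disease recurrence, so it is a DFS event.

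**The concern.** Take a subject diagnosed with a colon cancer at month 30, which the investigator thinks unrelated to study drug. The malignancy bullets require an SAE report. The 130-day sentence and Table 7-1 say not to send one. Two sites can handle the same case differently and both point to the protocol.

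The AESI table applies the same time cut, so it cannot show this case even where the site did report it. New cancers usually take time to appear, and the trial exists because earlier data suggested that the drug changes cancer incidence (Protocol 2.1). Protocol 1.3.1.1.3 adds that long-term animal carcinogenicity studies were not done. For this AESI, a table that ends soon after treatment, followed by reporting that depends on a causality opinion, is a weak basis for comparing arms. It also leaves room for the safety tables and SAP 2.7.3 to show different numbers of cancers with no planned reconciliation.

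**Working it through.** **1. Do the rules conflict?** The bullets could be read as saying only that a new cancer is serious, leaving timing to the 130-day sentence. Protocol 8.2.1 already classes new malignant neoplasms as serious, so on that reading the bullets in 8.2.2 would add little. Their stated subject is reporting. The conflict stands. A further rule in 8.2.2 (also in 7.1.6.1 and 8.1.1) limits collection to related SAEs once a new antineoplastic therapy starts after study treatment ends. That can collide with the bullets even inside 130 days.

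**2. Where the window closes.** There are 18 doses, 21 days apart, so the last dose falls 17 × 21 = 357 days after the first. Adding 130 gives 487 days, and 487 / 30.4375 = 16.0 months.

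**3. Reproduce the plan's follow-up model.** Inputs from Protocol 10.8: 1500 subjects, 30 months of uniform accrual, placebo median DFS 48 months, hazard ratio 0.716, 5% yearly dropout, analysis at month 42. Follow-up f is then uniform from 12 to 42 months.

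- Monthly hazards: placebo ln 2 / 48 = 0.01444; canakinumab 0.716 × 0.01444 = 0.01034; dropout −ln(0.95) / 12 = 0.00427.
- Events per arm = 750 × λ/(λ+η) × mean of [1 − exp(−(λ+η) f)], where λ is the event hazard and η the dropout hazard.
- Result: 225 + 170 = 395 DFS events, against 392 stated.
- The same model with the OS inputs of Protocol 10.9 (median 66 months, hazard ratio 0.776, 3% yearly loss) gives 318 deaths at month 42 (318 stated) and 507 at month 63 (504 stated).

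The model matches the plan, so it is a fair basis for person-time.

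**4. Share of person-time after month 16.0, at month 42.** Share = 1 − mean[I(min(f, 16))] / mean[I(f)], with I(x) = x if there is no attrition and I(x) = (1 − exp(−hx)) / h for removal hazard h.

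- *No attrition:* mean follow-up is 27 months. Inside the window: 14 × 4/30 + 16 × 26/30 = 15.73 months. Share = 1 − 15.73/27 = 42%.
- *Survival follow-up* (pooled OS hazard 0.00933 + loss 0.00254): mean 22.8 months, share 37%.
- *Disease-free follow-up* (pooled DFS hazard 0.01239 + dropout 0.00427): mean 21.3 months, share 35%.

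These assume that everyone receives all 18 doses. If 20–40% stopped within a year (an assumption), the two follow-up shares would rise to 40–46%.

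**5. At the close-out cut-off of 07 Feb 2023.** The amendment rationales give 63 randomized by 11 Dec 2018, 507 by 05 Feb 2020, 1234 by 01 Sep 2021 and 1382 in total. Assumed: first randomization in mid-March 2018 and last in about January 2022 (screening ended on 07 Dec 2021). Interpolating, mean potential follow-up is 31.9 months. The share after the window is 50% without attrition, 44% on survival follow-up and 42% on disease-free follow-up.

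**6. From person-time to cancers.** If the rate of new primaries is constant over time, these are also the expected shares of new primaries arising after the window. If the rate rises with time, the shares are larger.

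**7. What the other routes add.** SAP 2.7.3 gives number of subjects, site, histology, staging, metastatic sites and time to diagnosis, but no rate over follow-up. DFS merges new lung primaries with recurrence and counts only the first event. No step reconciles either source with the AESI table.

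**The case against.** A reader could go further and infer that a third to a half of new cancers will be missing from the trial. The documents do not support that. Non-lung primaries have their own eCRF page and table, timed from randomization. New lung primaries are DFS events, and imaging runs for up to five years, continuing even after a new antineoplastic therapy starts. Later antineoplastic therapies are recorded through survival follow-up, all deaths are summarized, and post-treatment safety data that were collected are listed. All of this stands.

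It is also fair that SAP 2.1 makes summaries by treatment arm the default, so 2.7.3 need not be faulted for failing to repeat it. By-arm counts in a 1:1 trial can be interpreted. It would therefore be too strong to say that the plan cannot characterise malignancy at all, particularly as more than half of person-time at month 42 lies inside the window. The 130 days also have a stated basis, about five half-lives, which suits most adverse events.

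A reader might also quote 1 − 16/60 = 73% as the share outside the window. That needs five full years on every subject. At the planned month-42 analysis, mean follow-up cannot exceed 27 months (2.25 years).

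None of this removes the contradiction in 8.2.2 or the cut in the AESI table. The other routes mean that the data can be recovered. They do not make the safety reporting consistent.

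**Conclusion.** The point holds as an inconsistency in reporting and a restriction in analysis, not as lost data. Protocol 8.2.2 gives two rules for a new primary after day 130 that cannot both be followed, and the SAP's Malignancy AESI count ends at 130 days after last dose. About 35–42% of person-time at the month-42 DFS analysis, and about 42–50% at close-out, lies beyond that point. A similar share of new primaries can be absent from the AESI table and, where judged unrelated, from SAE reporting. Those shares rest on a constant cancer rate, full dosing and, for close-out, the assumed accrual dates.

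The practical consequence is that the AESI table, the SAE reports, SAP 2.7.3 and the DFS records can each give a different malignancy count, and none gives a rate per subject-year by arm over all follow-up. It should be corrected. It does not bear on the primary or key secondary test.

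**What to change.** 1. **Protocol 8.2.2 and Table 7-1:** reconcile the malignancy bullets, the 130-day sentence, the new-antineoplastic-therapy sentence and the post-treatment adverse-event row, so that one explicit rule governs new primary malignancies after day 130. One way is a stated exception to the 130-day rule.
2. **SAP 2.8.1.1:** beside the on-treatment Malignancy count, add a summary over all follow-up by arm, giving number of subjects and rate per 100 subject-years. Reconcile it with SAP 2.7.3 and with the new lung primaries in the DFS records.

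**Cost.** One extra table, built largely from data already collected, and some additional SAE forms if an exception is adopted. For scale, assume the placebo rates in Protocol Table 2-1: any cancer 1.88 per 100 subject-years, or 1.88 − 0.49 = 1.39 without lung. That population differs from this one.

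- Month 42, survival follow-up: 1500 × 22.8/12 × 0.37 ≈ 1,054 subject-years after the window, or about 15 to 20 cancers.
- Close-out, no attrition: 1382 × 31.9/12 × 0.502 ≈ 1,844 subject-years, or about 26 to 35.

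That is a few dozen forms at most. No dose, endpoint or hypothesis test changes.
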